2.2 Secondary Objective

- Evaluate safety and tolerance of the Orbera intragastric balloon and concomitant paired EUS guided liver biopsy at time of balloon placement and removal.
- Obtaining lipid saturation (SI) and polyunsaturation (PUI) indices via H-MRS technology pre- and post-intervention
- Obtaining hepatic triglycerides content (HTGC) via H-MRS technology pre- and post-intervention.
- Obtaining percent unsaturated fatty acyl chains present in this cohort of NASH patients, as well as changes that occur in the setting of weight loss.
- Obtaining percent polyunsaturated fatty acyl chains present in this cohort of NASH patients, as well as changes that occur in the setting of weight loss.
- Measurement of hepatic lipid composition by needle biopsy and lipidomic analysis techniques before and after weight loss.
- Correlation of MRS obtained lipid composition to lipidomic analysis composition.

3 Study Design

3.1 General Design

Patients with suspicion for NASH at our center undergo a combined MRE/MRS (magnetic resonance elastography/magnetic resonance spectroscopy) sequence to classify their disease according to four stages. These stages are numbered from 1-4 with stage 4 signifying more advanced fibrosis. The MRE/MRS sequence also quantifies hepatic fat content. Those with stage 1-3 fibrosis will be referred for IGB placement for weight loss as a management strategy for NASH. Once referred to the endoscopic bariatric clinic a multidisciplinary team that includes endocrinology, gastroenterology, psychology, and nutrition will evaluate them. If found to be appropriate candidates, they will be enrolled in this study by a member of the study team who will discuss the study protocol, risks, benefits, and alternatives with patients and have them sign an informed consent. Patient will undergo intragastric balloon placement and an EUS guided liver biopsy during the same endoscopy session will be performed under monitored anesthesia sedation at our outpatient endoscopy unit. The EUS guided liver biopsy will be performed before balloon insertion from the left liver lobe under EUS guidance using a 22 gauge core needle (Sharkcore, Covidien, Minneapolis, MN). Three passes will be performed from two separate liver segments (Figure 2). An additional pass may be performed at the discretion of the PI if the three performed passes do not yield enough tissue on visual inspection of the core to ensure adequate histology analysis. The maximum number of passes will not exceed four. Doppler ultrasound will be used to exclude intervening vessels. Two samples will be submitted for histopathology review in formalin, and one or two will be submitted for total fat

Of note in this protocol will include patients with diagnosis of NASH with fibrosis (stage 1-3) on MRE/MRS (magnetic resonance elastography/magnetic resonance spectroscopy), which has demonstrated high accuracy in making the diagnosis, but has unknown sensitivity and specificity to detect change over time and has no standardized validated criteria to objectively assess improvement in NASH and fibrosis as exists for liver biopsy, which remains the gold standard in clinic trial evaluating the impact of intervention on NASH. **In the rare instance that the MRE result was falsely positive and the patient was not found to have NASH on liver biopsy. The patient will continue with balloon therapy for weight loss, but we will not repeat liver biopsy at 6 months, since the balloon is indicated for obesity with or without NASH with clear health benefits to weight loss in this cohort.** The balloon cost will remain covered by the study under these rare circumstances.

3.2 Primary Study Endpoint

Number of subjects with ≥ 2 points improvement in NASH activity scores on paired liver biopsies before and 6 months after intragastric balloon placement.

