8.4.1	Sponsor-Investigator Reporting, Notifying Mayo IRB.....	27
8.4.2	Sponsor-Investigator Reporting: Notifying the FDA.....	27
8.5	UNBLINDING PROCEDURES	28
8.6	STOPPING RULES.....	28
8.7	MEDICAL MONITORING	28
8.7.1	Internal Data and Safety Monitoring Board	28
8.8	CONFIDENTIALITY.....	29
8.9	SOURCE DOCUMENTS.....	29
8.10	CASE REPORT FORMS	29
8.11	RECORDS RETENTION	30
9	STUDY MONITORING, AUDITING, AND INSPECTING	30
9.1	STUDY MONITORING PLAN	30
9.2	AUDITING AND INSPECTING	31
10	ETHICAL CONSIDERATIONS	31
11	STUDY FINANCES	31
11.1	FUNDING SOURCE	31
11.2	SUBJECT STIPENDS OR PAYMENTS	31
12	PUBLICATION PLAN	31
13	REFERENCES	32

LIST OF ABBREVIATIONS

AE	Adverse Event/Adverse Experience
BMI	Body Mass Index
CFR	Code of Federal Regulations
CRF	Case Report Form
DSMB	Data and Safety Monitoring Board
EUS	Endoscopic Ultrasound
FDA	Food and Drug Administration
GCP	Good Clinical Practice
HIPAA	Health Insurance Portability and Accountability Act
IDE	Investigational Device Exemption
IGB	Intragastric Balloon
IRB	Institutional Review Board
MRE	Magnetic Resonance Elastography
MRS	Magnetic Resonance Spectroscopy
NAFLD	Non-alcoholic Fatty Liver Disease
NAS	Non-alcoholic Steatohepatitis Score
NASH	Non-alcoholic Steatohepatitis
PHI	Protected Health Information
PI	Principal Investigator
SAE	Serious Adverse Event/Serious Adverse Experience
SOP	Standard Operating Procedure
TBWL	Total Body Weight Loss
UADE	Unanticipated Adverse Device Effect

Study Summary

Title	A Pilot Combined Endoscopic Ultrasound Guided Core Liver Biopsy and Intragastric Balloon Placement for Management of Nonalcoholic Steatohepatitis and Obesity
Running Title	EUS and IGB for Management of NASH and Obesity
IRB Protocol Number	15-009262
Phase	Pilot
Methodology	Open Label

Overall Study Duration	60-64 Weeks
Subject Participation Duration	12 months
Objectives	Significant weight loss achieved with the IGB in NASH patients with BMI between 30 – 55 kg/m ² and early fibrosis based on MRE is associated with ≥ 2 points improvement in NAS and regression of fibrosis on paired EUS guided liver core biopsies.
Number of Subjects	25
Diagnosis and Main Inclusion Criteria	Inclusion criteria to our study include NASH patients with evidence of early fibrosis (excluding advanced fibrosis or cirrhosis) by baseline liver biopsy when available, and/or MRE (magnetic resonance elastography), who are referred for an intragastric balloon placement for weight loss.

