Study Device	Orbera Intragastric Balloon (Apollo Endosurgery Austin, TX)
Duration of Exposure	6 months
Statistical Methodology	We have the resources to enroll at total of 20 patients (additional 5 in case of early withdrawal) to this study. With a sample size of 20 we will have 80% power to detect a medium to large (effect size 0.66) improvement in NASH activity scores on paired liver biopsies using a paired t-test with a two sides p-value < 0.05. The table below shows that sample size needed to detect small, medium, or large improvement in NAS scores on paired liver biopsies at 80% power.

1 Introduction

This document is a protocol for a human research study. This study will be carried out in accordance with the procedures described in this protocol, applicable United States government regulations and Mayo Clinic policies and procedures.

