6.3 Tissue lipidomics workup

A total of 50 mg of liver tissue will be collected via EUS-guided biopsy. Sharkcore needle is 22 gauge. Diameter is ~0.7 mm. ~270 mm of tissue length will be acquired and will deliver a volume of ~50 mg. The sample will be frozen in liquid nitrogen immediately upon harvesting in the endoscopy suite and placed in a 1.5 conical Eppendorf tube. Samples shall not sit more than few minutes before flash freezing to ensure adequate analysis. Also, inspection before freezing will occur to ensure that the tissue is relatively clean specimen on inspection.

7 Statistical Plan

Baseline subject characteristics will be described by their means, medians and and/or frequencies. For our primary study endpoint of improvement in NASH activity scores on paired liver biopsies at baseline and after 6 months, we will be using a paired t-test with two sided alpha <0.05. With a sample size of 20 subjects, we will have 80% power to detect a medium to large difference in activity scores (0.66). Please see table below for minimum sample size needed for each desired effect size.

	Small effect size 0.5	Medium effect size 0.66	Large effect size 0.8
Sample (N)	34	20	15

Additionally, we will run a linear regression analysis with the change in NASH activity scores as the outcome with baseline BMI and diabetes as the covariates on a univariable and multivariable fashion to investigate their effects on the primary outcome.

For our secondary endpoint of number of subjects with regression of fibrosis in paired liver biopsies, we will be reporting the percentage of subjects with regression. As far as the secondary endpoint of percent total body weight 6 months after Orbera balloon placement, we will be reporting the mean or median percent total body weight loss at 6 months.

For our secondary endpoint of quantifying total fat liver and triglycerides content, we will be reporting the mean and median percent of change at 6 months.

8 Safety and Adverse Events

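### The primary endpoint is a count of subjects with a NAS improvement of at least 2 points, but section 7 analyses and powers the mean change in NAS and plans no estimate for the count

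*Combined protocol and SAP*

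**What the plan says.** Section 3.2 has a single entry, a responder count: "Number of subjects with ≥ 2 points improvement in NASH activity scores on paired liver biopsies", comparing before balloon placement with 6 months after. The Study Summary objective uses the same 2-point threshold ("early fibrosis based on MRE is associated with ≥ 2 points improvement in NAS and regression of fibrosis"), as does Hypothesis 1 in section 2.1.

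Section 7 describes the endpoint differently: "For our primary study endpoint of improvement in NASH activity scores on paired liver biopsies at baseline and after 6 months", followed by "we will be using a paired t-test with two sided alpha <0.05". The threshold appears nowhere in section 7. The sample size rests on the same test: "we will have 80% power to detect a medium to large difference in activity scores (0.66)". The Study Summary repeats it: "With a sample size of 20 we will have 80% power to detect a medium to large (effect size 0.66) improvement". Section 7 also plans linear regressions of the change in score on baseline BMI and diabetes, "to investigate their effects on the primary outcome".

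The only subject-level proportion in section 7 is for a secondary endpoint, fibrosis regression: "we will be reporting the percentage of subjects with regression". Nothing comparable is planned for the primary count.

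**The concern.** A count of responders and a mean change are different quantities, and a paired t-test cannot produce the first. With two sections naming different primary endpoints, the primary result is not fixed in advance in an open-label, single-arm study. A significant t-test does not determine the responder rate, and the power statement says nothing about how precisely that rate will be estimated. Section 12 also commits to posting results within a time limit tied to the primary outcome, so which outcome that is has to be clear.

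The count also needs a denominator. Under section 3.1, subjects found not to have NASH on biopsy get no second biopsy. Under section 4.4.1, up to 5 withdrawn subjects may be replaced. The same number of responders gives a different rate depending on who is counted.

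**Working it through.** **Inputs from the documents.** N = 20, two-sided alpha 0.05, paired t-test, standardised effect 0.66, and a table giving N = 34, 20 and 15 for effects 0.5, 0.66 and 0.8 (section 7); threshold of 2 points (section 3.2).

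**Assumed.** The SD of the paired change is not given. The NAS SDs of 0.75 and 2.25 quoted from the earlier balloon study (sections 1.1, 1.4 and 1.5.1) are SDs of scores, not of change. I use SDs of change from 1 to 3 points and a normal model.

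**Step 1: reproduce the plan's figure.** Power is taken from the noncentral t with n − 1 degrees of freedom and noncentrality d√n.

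- n = 34, d = 0.5: 0.808
- n = 20, d = 0.66: noncentrality 0.66 × √20 = 2.95, power 0.7995
- n = 15, d = 0.8: 0.821

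The table is a sound paired t-test table. The arithmetic is not at fault; it describes mean change.

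**Step 2: put 0.66 SD on the NAS scale.** The powered mean change is 0.66 × SD. It reaches 2 points only at SD = 2/0.66 = 3.03. The smallest observed mean change giving p < 0.05 with 20 pairs is t(0.975, 19)/√20 = 2.093/4.472 = 0.468 SD.

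**Step 3: responder share at the powered effect.** The share is P(change ≥ c), with change normal with mean 0.66 SD. Take c = 1.5 if changes are rounded to whole points, or c = 2 with no rounding. The last column is from 200,000 simulated trials of 20 with rounded changes, keeping those with a significant improvement.

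| SD of change | Powered mean change | Smallest significant mean change | Share ≥ 2 points, rounded | Share ≥ 2 points, unrounded | Central 95% of responder counts (of 20) |
|---|---|---|---|---|---|
| 1 | 0.66 | 0.47 | 20% | 9% | 1–8 |
| 1.5 | 0.99 | 0.70 | 37% | 25% | 4–12 |
| 2 | 1.32 | 0.94 | 46% | 37% | 6–14 |
| 2.25 | 1.49 | 1.05 | 50% | 41% | 7–14 |
| 2.5 | 1.65 | 1.17 | 52% | 44% | 7–15 |
| 3 | 1.98 | 1.40 | 56% | 50% | 8–16 |

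**Step 4: the case where the true mean change is 2 points.** Across the same SDs, t-test power runs from over 99% (SD 1) down to 81% (SD 3). The responder share is 69% down to 57% with rounding, and 50% at every SD without. Here the two measures will usually point the same way.

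**Step 5: an extreme case.** If 4 subjects improve by 1 point and 16 do not change, t = 2.18 and p = 0.042 with 0 of 20 responders. This is possible but unlikely: zero responders occurred in about 0.5% of significant simulated trials at SD 1 and in essentially none from SD 1.5 upward.

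**Step 6: precision of the endpoint in section 3.2.** Exact (Clopper-Pearson) 95% intervals at n = 20:

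- 5/20: 9% to 49%
- 10/20: 27% to 73%
- 15/20: 51% to 91%

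**The case against.** The strongest reply is that this is a single-arm pilot with no comparator and no reference responder rate. A count can be reported descriptively with no test, section 7 names one test only, and no patient, procedure or sample size would change. That bears on the cost of the repair, but not on whether the plan contradicts itself: section 7 attaches the words "primary study endpoint", the alpha and the 80% power to a quantity that section 3.2 does not define.

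Some narrower points stand:

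- The Summary objective and Hypothesis 1 share the threshold but do not mention a number of subjects. They could be read as a mean improvement of at least 2 points. Only section 3.2 clearly states a count.
- Because section 3.2 refers to paired biopsies, evaluable pairs is a natural reading of the denominator. It is still nowhere stated.
- The responder shares rest on assumed SDs and a normal model. The low values arise at the powered effect with small SDs, not at a 2-point mean change.
- Intervals quoted for 20 subjects hold only if the denominator is 20. If it were 25, 10 responders would give 21% to 61%.

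None of these reconciles section 3.2 with section 7.

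**Conclusion.** The concern holds, and it must be fixed because it concerns which result is primary. The sample-size calculation is correct for mean change (power 0.7995 at 20 pairs) but does not describe the responder count. At the powered effect, the responder share could be anywhere from about 20% to 56% with rounding, or 9% to 50% without, for SDs of change from 1 to 3 points. The practical gap is small if the true mean change is near 2 points and grows as the change gets smaller. The mismatch between sections and the exact intervals do not depend on the assumed SDs; the responder shares and simulated counts do.

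**What to change.** In section 7, make the primary analysis the proportion of subjects with a NAS improvement of at least 2 points, with an exact 95% confidence interval and a named denominator. The denominator should say how it treats subjects with no second biopsy because NASH was not found, and withdrawn or replaced subjects. One option is all subjects with NASH on the baseline biopsy, counting a missing second biopsy as no improvement, with evaluable pairs as a sensitivity analysis. Keep the paired t-test and the regressions as named supportive analyses of mean change.

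In section 7 and the Summary, say that the 80% power at 0.66 applies to mean change with 20 evaluable pairs. Add the expected precision of the proportion: the intervals in step 6 if the denominator is 20, recalculated if the chosen denominator can differ.

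If the sponsor prefers mean change as primary, change section 3.2 instead, make the Summary objective and Hypothesis 1 say so explicitly, and keep the count as a secondary endpoint with its exact interval.

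Either route costs wording and one calculation, with no extra patients or procedures. The downside of the first is that the primary result becomes an estimate with a wide interval, which looks less favourable than the 80% power figure, although that figure remains true for mean change.

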3.3 Secondary Study Endpoints

- Regression of fibrosis on paired EUS guided liver core biopsies.

- Percent total body weight loss at 6 months after Orbera balloon placement.
- Obtaining lipid saturation (SI) and polyunsaturation (PUI) indices via H-MRS technology pre- and post-intervention
- Obtaining hepatic triglycerides content (HTGC) via H-MRS technology pre- and post-intervention.
- Obtaining percent unsaturated fatty acyl chains present in this cohort of NASH patients, as well as changes that occur in the setting of weight loss.
- Obtaining percent polyunsaturated fatty acyl chains present in this cohort of NASH patients, as well as changes that occur in the setting of weight loss.
- Measurement of hepatic lipid composition by needle biopsy and lipidomic analysis techniques before and after weight loss.
- Correlation of MRS obtained lipid composition to lipidomic analysis composition

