The degree of lipid saturation and polyunsaturation can be measured noninvasively by proton magnetic resonance spectroscopy [19]. This technique adds no cost, as the series can be simultaneously captured during MRE acquisition session, adding few minutes to the procedure. Evidence suggests that depletion of hepatic polyunsaturated fatty acids (PUFAs) reduces hepatic fatty acid oxidation and triglyceride export. Furthermore, it is associated with augmentation in in hepatic fatty acid and triglyceride synthesis, leading to increased triglyceride aggregation. Moreover, this process has been thought to increase inflammation and facilitates the development of steatohepatitis. Indeed, studies have shown that alterations

in tissue lipid saturation may portend sinister clinical outcomes more reliably than simple means of fatness measurements [20].

To the best of our knowledge, no studies have corroborated the sensitivity of H-MRS detection of SI and PUI changes, as well as other indices of hepatic lipid composition, with weight loss, and its correlation to decrease in total steatosis, changes in liver stiffness, as well as changes in fibrosis scores on histology.

Our current study offers a rare window to accurately examine and capture these changes due to the availability of liver tissue histology pre- and post-intervention. This will allow the determination H-MRS reliability in predicting lipidomic analysis changes in a NASH afflicted liver, obviating the need of invasive testing.

Furthermore, an unmet need in the understanding of nonalcoholic fatty liver disease is the determination of the interactions between the changes in hepatic lipid polyunsaturated fatty acids (PUFA) depletion and liver injury; considering the expected improvement in liver histology parameters with our proposed intervention, our study would offer a unique opportunity to correlate these improvements with PUFA depletion[19, 21, 22].

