1.5.3 Potential Benefits

Hepatic fibrosis regardless of etiology progresses to cirrhosis if the etiological agent is not removed or treated. [5] There is growing evidence for reversibility of steatohepatitis and hepatic fibrosis especially in early stages and with significant weight loss. [5] In a seminal study of 293 patients with histologically proven NASH who had life-style modification to reduce their weight over 52 weeks, 72 (25%) achieved resolution of steatohepatitis, 138 (47%) had reductions in nonalcoholic fatty liver disease activity score (NAS), and 56 (19%) had regression of fibrosis. [5] The degree of weight loss was independently associated with improvements in all NASH-related histologic parameters with all patients who lost $\geq 10\%$ of their total body weight (%TBWL) had reductions in NAS, 90% had resolution of NASH, and 45% had regression of fibrosis, compared to 32% (reduction in NAS), 10% (resolution of NASH), and 16% (regression of fibrosis) in those who lost $\leq 5\%$. Life-style interventions for obesity; however, are associated with poorly sustained effects and relatively weak efficacy. Indeed, in this study less than 10% of the cohort achieved $\geq 10\%$ TBWL with life-style modification alone and the majority (70%) achieved less than 5% TBWL.[5]

The Orbera intragastric balloon is expected to results in 12.3% (95% CI, 7.91–16.73), 13.16% (95% CI, 12.37–13.95), and 11.27% (95% CI, 8.17–14.36) TBWL at 3, 6, and 12 months after implantation, respectively.[6] This was based on a review of 55 studies. This balloon is currently FDA approved for use in the United States after a US randomized multicenter pivotal trial demonstrated similar efficacy. Thus, with the anticipated weight loss seen with the Orbera Intragastric balloon, we expect improvement in histological NASH parameters and regression of fibrosis with the weight loss achieved with the intragastric balloon.

The ability to quantify and capture hepatic fat change, and correlate it to spectroscopic changes could offer important non-invasive means of NASH progression/regression in afflicted individuals. This study would offer a unique opportunity to corroborate the utility of MRS in accurate and reliable evaluation of this parameter.

2 Study Objectives

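### A correlation alone cannot show that MRS predicts tissue lipid composition well enough to spare biopsy, and Section 7 gives no analysis for that endpoint

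*Combined protocol and SAP*

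**What the plan says.** Section 1.5.1 sets the aim for the spectroscopy work: "This will allow the determination H-MRS reliability in predicting lipidomic analysis changes in a NASH afflicted liver, obviating the need of invasive testing". Section 1.5.3 adds that the study could "corroborate the utility of MRS in accurate and reliable evaluation of this parameter".

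The only comparison of MRS with tissue is the last item in the lists of secondary objectives (2.2) and secondary endpoints (3.3): "Correlation of MRS obtained lipid composition to lipidomic analysis composition".

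Section 7 does not mention this endpoint. For liver fat and triglyceride content it says only that "we will be reporting the mean and median percent of change at 6 months". The one significance level in the plan belongs to the primary endpoint: "we will be using a paired t-test with two sided alpha <0.05". For the MRS comparison the documents name no coefficient, test or acceptable error. They do not say whether baseline values, Month 6 values, pooled values or changes are to be correlated. No analysis of bias, agreement or calibration appears anywhere.

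**The concern.** The aim and the analysis do not match. To spare a patient a biopsy, one needs to know how far that patient's MRS-based value may lie from the tissue value, and whether MRS is systematically off. A correlation answers a different question: whether the two measures rise and fall together across patients. An MRS index that tracks tissue closely but reads at half scale, or that is noisy for individuals, can still show a respectable r.

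At stake is the strength of the MRS conclusion. Followed as written, the plan cannot detect an offset or scale error and does not quantify individual prediction error. Nothing in it prevents a non-zero correlation from being reported as validation.

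**Working it through.** **The plan's own figure.** Section 7 gives N = 20 for 80% power at a standardised paired effect of 0.66, two-sided 0.05. The exact paired t-test gives 79.95% power at N = 20, so the figure reproduces. The exact sample sizes for effects 0.5, 0.66 and 0.8 are 34, 21 and 15, against 34, 20 and 15 in the table. This concerns the NASH activity score; no figure is given for the MRS endpoint.

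**Inputs**
- From the documents: 20 patients, with up to 5 more for withdrawals (Study Summary: "We have the resources to enroll at total of 20 patients (additional 5 in case of early withdrawal) to this study").
- Assumed, because the documents give no value: true correlation ρ from 0.3 to 0.9; MRS offset of 0 or +2 between-patient SD; MRS scale of 1 or 0.5; bivariate normal data; and, for step 2 only, a two-sided 5% test of r = 0.

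**Step 1. What r cannot see.** For any constants a and b > 0, corr(T, a + bM) = corr(T, M), where T is the tissue value and M the MRS value. Offset a and scale b drop out. For within-patient change, a cancels by subtraction but b remains: if ΔM = 0.5 ΔT exactly, then r = 1 although every change is reported at half its size.

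**Step 2. The default test, if it were used.** At n = 20 the critical value is |r| = t/√(t² + 18) with t = 2.101, so 2.101/√22.41 = 0.444. The share of simulated trials (40,000 per setting) with a significant r was:

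| True ρ | n = 20 | n = 25 | Residual SD of tissue given MRS, √(1 − ρ²), in tissue SDs |
|---|---|---|---|
| 0.3 | 25% | 31% | 0.95 |
| 0.5 | 64% | 75% | 0.87 |
| 0.6 | 84% | 91% | 0.80 |
| 0.7 | 96% | 98.5% | 0.71 |

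Fisher z check at n = 20, ρ = 0.6: atanh(0.6) × √17 − 1.96 = 0.693 × 4.123 − 1.96 = 0.90, which gives 81.5%, close to the simulated 84%. Adding the offset, the half scale or both left every rate unchanged. A rate of 95% needs ρ of about 0.70 at n = 20, or 0.65 at n = 25. The last column shows that a usually significant correlation can leave most of the between-patient spread unexplained.

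**Step 3. What other summaries would show.** Take ρ = 0.9, where the test of r = 0 is significant in about 100% of trials in all four cases. In units of the tissue SD, the concordance coefficient is 2ρs/(1 + s² + d²), with s the MRS SD and d the offset. The calibration slope of tissue on MRS is ρ/s.

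| MRS error | Concordance | Slope |
|---|---|---|
| None (s = 1, d = 0) | 1.8/2 = 0.90 | 0.9 |
| Half scale (s = 0.5, d = 0) | 0.9/1.25 = 0.72 | 1.8 |
| +2 SD offset (s = 1, d = 2) | 1.8/6 = 0.30 | 0.9, intercept lower by 0.9 × 2 = 1.8 SD |
| Both (s = 0.5, d = 2) | 0.9/5.25 = 0.17 | 1.8, intercept also altered |

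The correlation is 0.9 in every row; slope and intercept together, or concordance, tell the rows apart.

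**Step 4. Pooling the visits.** Suppose 40 values from 20 patients were pooled, both methods fell between visits, and there was no correlation within either visit. A shared fall of 1, 1.5 or 2 SD would then give a significant r in 24%, 67% or 96% of trials. The plan does not say that it will pool; it does not exclude it.

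**Step 5. Precision of the remedy.** The 95% half-width around each limit of agreement is t × √(1/n + 1.96²/(2(n − 1))). At n = 20 this is 2.093 × √(0.050 + 0.101) = 0.81 SD of the differences; at n = 25 it is 0.72.

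**The case against.** The strongest reply is that the plan never says a significant correlation will count as validation. The secondary endpoints that Section 7 does cover get descriptive summaries, so the natural reading is a descriptive r. This stands. A reader might infer that MRS will be judged by a test whose null is no association, and that a poor MRS would then pass almost every time, at 84% to 96% where 5% was intended. The documents do not support that. They contain no such rule, nothing in them marks ρ of 0.6 or 0.7 as inadequate, and rejecting r = 0 when ρ is 0.6 is a correct rejection of that null. Nor does almost every time hold for a very imprecise MRS, for which step 2 gives 25% at ρ = 0.3 and 64% at ρ = 0.5.

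Second, 1.5.1 speaks of predicting changes, which asks for less than interchangeable readings. A stable offset or scale error can be calibrated away, and an offset cancels in a change score. This also stands, and is why the fix leads with calibration. But calibration helps only if it is estimated and its error reported, and the plan does neither.

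Third, limits of agreement need common units, and 6.3 gives none for the lipidomic output. That restricts where they can be used. Fourth, 20 evaluable pairs are not assured, since 3.1 drops the second biopsy when NASH is not found; fewer pairs would lower the rates in step 2 and widen the intervals in step 5. Fifth, MRS is acquired in the MRE session (1.5.1), and 4.1 accepts an MRE within 6 months of enrollment, so a baseline difference could partly reflect elapsed time. None of these points makes a correlation answer the stated aim.

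**Conclusion.** The concern holds in this form: the stated aim is reliable prediction that would spare invasive testing, the only named comparison is a correlation, and Section 7 has no analysis for it. That a correlation is blind to offset and scale is algebra and needs no assumption. The significance rates (about 25%, 64%, 84% and 96% at ρ of 0.3, 0.5, 0.6 and 0.7) are illustrative. They rest on an assumed 5% test of r = 0, 20 pairs and bivariate normal data, and they are not error rates of any rule in the plan. The consequence is limited to a secondary endpoint of a pilot: the MRS conclusion would be weaker than the rationale suggests, while the primary histological result is unaffected.

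**What to change.** In 2.2, 3.3 and Section 7:

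- Make the main analysis a calibration regression of the lipidomic value on the MRS value. Report slope, intercept and prediction error with 95% confidence intervals, separately at baseline, at Month 6 and for the within-patient change. Do not pool the visits as if they were independent.
- Where both methods report in the same units, also give the mean difference and the 95% limits of agreement (Bland-Altman), with confidence intervals.
- Keep the correlation, with its 95% interval, as descriptive. State that a non-zero correlation will not be taken as evidence that MRS can replace biopsy.
- Report the interval between scan and biopsy, so that baseline differences can be read in that light.

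The cost is a few sentences and a small amount of analysis. MRE/MRS and liver biopsy are already scheduled at baseline and Month 6 (6.2), so no new procedures are needed. The downside is that, with about 20 pairs, each limit of agreement is known only to about ±0.8 SD of the differences. The result would be an estimate to plan a larger study from, and the claim for MRS in 1.5.1 and 1.5.3 would have to be worded more modestly.
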